1. INTRODUCTION

Cardiovascular (CV) disease is the leading cause of death worldwide, accounting for 30% of all deaths(1). High blood pressure (BP) is the most important individual factor contributing to global burden of disease worldwide (2), and as a consequence BP is the most important modifiable risk factor for CV disease. Prospective cohort studies have established a graded positive association between BP and the risk of CV disease, starting at 115 mmHg for systolic BP measured in the morning(3). The effectiveness of antihypertensive therapy was initially demonstrated in patients with systolic BP above 160 mmHg and the results of early prospective trials were reviewed two decades ago(4). More recently, the possibility of measuring BP out of the office has opened the investigation about the caveats of office BP measurements mainly consisting of white coat hypertension, masked hypertension, short-term BP variability, and nighttime BP, all these situations are characterized by an increase in CV and renal risk when compared to well controlled arterial hypertension(5, 6). The most relevant differences according to the accompanying risks is the one observed when daytime and nighttime BP levels are compared. Nighttime BP has shown to be the one accompanied by the highest level of risk when it is elevated(5). Data from the Spanish ABPM Registry(7) have shown that nighttime BP in albuminuric type 2 diabetics shows a significant difference when compared to values obtained in non-albuminuric type 2 diabetics. The same is true in non-diabetic patients with higher nighttime BP levels when albuminuria is present albeit not as much as in type 2 diabetics (7). According to our data, the differences in nighttime BP oscillates on average between 9-12 mmHg (7). Such a difference can account for the development of albuminuria as shown by Lurbe et al. type 1 diabetics(8). Both albuminuria and elevated nighttime BP are significant predictors of cardiovascular (CV) events and

deaths as well as of progression of chronic kidney disease (CKD)(5, 9), hence the control of nighttime BP could translate into a better CV protection and in a significant diminution of albuminuria if present.

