The newest class of drugs for type 2 are the sodium glucose co-transporter 2 receptor (SGLT-2) inhibitors. These reduce the reabsorption of renal-filtered glucose back into the bloodstream, thereby leading to loss glucose in the urine. The Figure 1 obtained from Rajasekeran et al. (10) shows the main mechanisms of action of these drugs mediated mainly through glycosuria and natriuresis.

[figure not shown]

Figure 1. Cardiorenal protection of SGLT2 inhibitors mediated by glycosuria and natriuresis. Obtained from Rajasekeran et al.(10)

Other protective effect directly related to the heart improving left ventricular function and diminishing left ventricular mass have been described for these drugs(11, 12). Recently, the Empagliflozin Cardiovascular Outcome and Mortality in Type 2 Diabetes (EMPA-REG) trial(13) demonstrated the capacity of empagliflozin to significantly reduce the relative risk for both CV mortality and all-cause mortality as well as hospitalizations due to heart failure in type 2 diabetic patients. The study also demonstrated the capacity of the drug to slow the progression of kidney disease in type 2 diabetic patients together with the finding of a significantly lower risk of clinically relevant renal events(14).

SGLT2 antagonists are drugs with the capacity to lower BP above the level obtained by commonly used antihypertensive drugs(15).The decrease in BP contributes importantly to the good effects observed in EMPA-REG study(13).Dapagliflozin also improves significantly BP and does it during 24 hours(16).

We have hypothesized that the capacity of dapagliflozin to lower BP could be particularly intense during nighttime. This in turn could participate in the observed decay in albuminuria. Should this hypothesis be confirmed, it could contribute importantly to the potential positive influence of all SGLT2 in preventing mortality and hospitalization due to heart failure as shown by the EMPA-REG study(13).

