2. OBJECTIVES

Primary Objective:

To investigate the effect of the addition of 10 mg daily of dapagliflozin to the treatment of diabetic patients compared to the addition of placebo on the change in nighttime blood pressure (measured by ABPM) over 12 weeks among patients with albuminuria levels ≥ 30 and < 3000 mg/g creatinine and estimated glomerular filtration rate ≥ 60 mL/min/1.73 m².

Secondary objectives:

- 1) To investigate the effect of the addition of 10 mg daily of dapagliflozin to the treatment of diabetic patients compared to the addition of placebo on the change in nighttime blood pressure (measured by ABPM) over 12 weeks in the subgroup of patients with high (30-300 mg/g creatinine) albuminuria levels.
- 2) To investigate the effect of the addition of 10 mg daily of dapagliflozin to the treatment of diabetic patients compared to the addition of placebo on the change in nighttime blood pressure (measured by ABPM) over 12 weeks in the subgroup of patients with very high (>300 mg/g creatinine) albuminuria levels.
- 3) Changes in albuminuria, office BP and HbA1C in the two subgroups of patients investigated

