3.8. END POINTS

Primary: Changes in mean nocturnal BP from baseline (week 0) to last visit (week 12).

Secondary:

- Changes in office BP from baseline (week 0) to last visit (week 12).
- Changes in HbA1C from baseline (week 0) to last visit (week 12).
- Changes in albuminuria from baseline (week 0) to last visit (week 12).
- Natural variability of mean nocturnal BP on separate visits (placebo group).

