3.9. VISITS, VARIABLES AND MEASUREMENTS

Four clinical visits are planned in every patient at 0 (recruitment and randomization), 4, 8 and 12 weeks. Information on personal and family history of disease, clinical examination (including office BP determination), ABPM and blood and urine samples will be obtained on visits 0. The variables measured in the blood and urine samples depend on the criterium of the attending physician. For this trial, only HbA1c, serum creatinine, estimated glomerular filtration rate (eGFR) and albuminuria are mandatory. All this information, except personal and family history of disease, will also be collected at week 12 (see “3.20. Conduct of the study”). Thirty days after the end of the medication (visit of week 12) all participants will be contacted by telephone to assess safety. For the initial laboratory data required in the CRF, data obtained in primary care in the previous 3 months could be valid. These data will be repeated at the end of the study. Informed consents for the study will be signed by the patients before coming to the hospital. Blood samples extractions included in this protocol will be done, handled and analyzed at each clinical setting according to usual clinical

practice. No blood sample storage will be needed in this study. Extra blood samples drawn will be handled as described in “3.23. Addendum”.

The relationship of the procedures performed at every clinical visit is presented below (see “3.20. Conduct of the study”). Case report forms (CRFs) are presented in Annex I. Albuminuria will be measured according to generally used and previously described methodologies(18-23).

ABPM will be measured using Mobil-o-Graph that will give us 24 hours brachial and central BP as well as pulse wave velocity and heart rate(24). As diary of activity of the patient will not be recorded, in this study, nocturnal (or nighttime) blood pressure refers to measurements within the period from 12.00 p.m. to 6.00 a.m.

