3.11. SAMPLE SIZE CONSIDERATIONS

For the main objective of the study, changes in mean nocturnal systolic blood pressure will be compared between the active treatment and placebo groups.

The use of SGLT2 inhibitors has been reported to be associated with reductions in office blood pressure of 4–8 mmHg, reductions that could be even higher with the use of ambulatory BP monitoring.¹⁵

Accepting an alpha error of 0.05 in a two-sided test, 150 patients are needed in the active treatment group and 75 in the placebo group (2:1 randomization) to have an 80% power (beta error=0.2) to detect as statistically significant a difference greater than or equal to 5 mmHg in mean nocturnal BP between placebo and active treatment (conservative estimate of the expected effect). The standard deviation is assumed to be 12 mmHg and it is expected a drop-out rate of 9%.

In the prespecified subgroup analysis by albuminuria levels, this sample size (75 in active treatment and 37 in placebo) allows to detect as statistically significant, within each albuminuria stratum and with the same assumptions and alfa and beta errors, a difference greater than or equal to 7,1 mmHg in the reduction of mean nocturnal BP between both groups (active treatment and placebo), an effect still within what can be expected.

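### Section 3.9 writes the night window for the primary endpoint as 12.00 p.m. to 6.00 a.m., literally noon to 6 a.m.; midnight was very probably meant and should be stated

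*Combined protocol and SAP*

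**What the plan says.** Section 3.8 names the primary endpoint: "Primary: Changes in mean nocturnal BP from baseline (week 0) to last visit (week 12"). It does not say which hours count as nocturnal. Section 3.9 does: "nocturnal (or nighttime) blood pressure refers to measurements within the period from 12.00 p.m. to 6.00 a.m". The same sentence explains that a fixed window is used because patients keep no activity diary, so the clock times alone decide which readings enter the mean. The device records for 24 hours, and the visit table in section 3.20 places ABPM at the hospital at visit 0 and at week 12.

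Other parts of the plan depend on this definition. Secondary objective 1 in section 2 concerns the "change in nighttime blood pressure (measured by ABPM) over 12 weeks in the subgroup of patients with high (30-300 mg/g creatinine) albuminuria levels", and secondary objective 2 is its counterpart above 300 mg/g. Section 3.8 also lists a secondary endpoint that uses the same mean: "Natural variability of mean nocturnal BP on separate visits (placebo group").

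One other clock period for night appears. The exclusion criteria in section 3.2 describe routine night work as work between 11.00 p.m. and 7.00 a.m. That serves eligibility and does not define the endpoint.

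**The concern.** The definition contradicts the term it defines. A period that starts at noon takes in the whole afternoon and evening and leaves out only the six hours from 6 a.m. to noon. The introduction treats day and night as different quantities ("The most relevant differences according to the accompanying risks is the one observed when daytime and nighttime BP levels are compared"), and the primary objective concerns night alone.

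The rule can also be carried out as written. Afternoon and evening readings will be present in every 24-hour recording, so entering the stated times in the ABPM software or the analysis code would give a plausible mean and no obvious error. At stake is whether the reported primary result is a change in nighttime BP or a change in something else.

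**Working it through.** **The plan's own figure.** The sample size in section 3.11 can be reproduced, and the window plays no part in it. Inputs from 3.11: difference 5 mmHg, SD 12 mmHg, two-sided alpha 0.05, power 80%, allocation 2:1, drop-out 9%.

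- Placebo n = (1 + 1/2) × (1.960 + 0.842)² × 12² / 5² = 67.8, rounded up to 68
- Active n = 2 × 68 = 136
- With drop-out: 68 / 0.91 = 74.7, so 75; 136 / 0.91 = 149.5, so 150
- Total 225, as stated

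No window length enters this formula, so restating the window leaves N unchanged.

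**Length of the window.** The limits come from section 3.9 and the comparison period from section 3.2.

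| Reading | Clock hours | Length |
|---|---|---|
| Literal, section 3.9 | 12:00 to 06:00 next day | 18 h |
| Starting at midnight | 00:00 to 06:00 | 6 h |
| Night-work period, section 3.2 | 23:00 to 07:00 | 8 h |

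- Literal hours before midnight: 12 / 18 = 67%
- Literal hours from midnight to 6 a.m.: 6 / 18 = 33%
- Literal hours outside the night-work period (noon to 11 p.m.): 11 / 18 = 61%

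Midnight to 6 a.m. lies wholly inside the night-work period. A window starting at noon cannot.

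These are shares of clock hours. They are also shares of readings only if readings are equally spaced, which section 3.9 does not state.

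**What an 18-hour mean would show.** With equal weight per hour (an assumption), the treatment contrast over the literal window is (6 × night + 12 × other) / 18. Three invented pairs of effects, in mmHg:

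- 9 at night, 3 otherwise: (54 + 36) / 18 = 5.00
- 5 at night, 5 otherwise: (30 + 60) / 18 = 5.00
- 1 at night, 7 otherwise: (6 + 84) / 18 = 5.00

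The same 18-hour result fits a large, a moderate or a very small effect at night, so it cannot stand in for the night-time contrast.

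**The case against.** The strongest reply is that the sentence corrects itself. It defines a nocturnal period, 12.00 p.m. is a common slip for midnight, and the night-work criterion and the day/night contrast in the introduction point the same way. Nothing in the documents shows that anyone planned or programmed an 18-hour window, and Annex I might state it correctly. The 24-hour recordings keep the night readings in any case, so a mistake could be undone. All of this stands, and it limits the weight of the point. It does not remove it: this is the only operational rule for the primary endpoint in the available text, and someone must turn it into numerical limits. If those limits are settled only after data are seen, the window becomes a post hoc choice.

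Three stronger readings are tempting, and the documents support none of them.

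- *The trial would lose power.* Section 3.11 cites only a class figure for office BP ("The use of SGLT2 inhibitors has been reported to be associated with reductions in office blood pressure of 4–8 mmHg"). The documents give neither the ambulatory contrast with placebo outside the night nor the SD of an 18-hour mean. Neither the direction nor the size of any effect on power can be determined.
- *The literal window would defeat the test of the trial's hypothesis.* The introduction says: "We have hypothesized that the capacity of dapagliflozin to lower BP could be particularly intense during nighttime". That is a comparison of night with day. Sections 2, 3.8 and 3.13 contain no such comparison, so a correct window would not test it either. The harm is to the primary objective.
- *Sections 3.2 and 3.9 conflict because their limits differ.* The two periods serve different purposes, so different limits are not in themselves an error.

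**Conclusion.** The point holds as a notation error in the definition of the primary endpoint. As written, the window is 18 hours, 12 of them (67%) before midnight, and this contradicts the term it defines. Midnight was very probably meant, which would make it 6 hours. The harm is conditional: it arises only if the times are applied literally, and it would then be the measurement of a different quantity in the primary endpoint, in secondary objectives 1 and 2 and in the nocturnal variability endpoint.

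This rests on the usual convention that 12 p.m. is noon, and on the absence of a correction in the available text, which does not include Annex I. That most averaged readings would come from before midnight also assumes roughly even spacing of readings. The correction should be made, because the defect sits in the primary endpoint and is almost free to remove.

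**What to change.** Before any data are analysed, the sponsor should:

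1. confirm which window was intended;
2. restate it in section 3.9 in 24-hour clock, as 00:00 to 06:00 if midnight is meant;
3. apply the same limits in ABPM processing at all three hospitals, for both the week 0 and the week 12 recordings.

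The cost is one phrase in section 3.9 and a settings check at three hospitals. No new data are needed, and the recordings and N = 225 are unchanged.

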3.10. WITHDRAWAL OF PATIENTS FROM THE STUDY AND UNBLINDING

Any patient can be withdrawn from the study at anytime during follow-up based on medical criteria of attending physician. The latter will detail the reasons of the withdrawal and communicate it urgently to the coordinating office of the trial if needed. If the reason for withdrawal is an adverse event (AE), the patient will be followed according to the procedures described for AEs (3.16).

Any patient can decide to abandon the study at any time during the study.

Withdrawal from the trial for any reason is definitive. When leaving the study, the main reason will be recorded and, if possible, the patient should have a final exam with the content of the visit of week 12. Patients that abandon the study will not be substituted.

All the above mentioned situations cause unblinding of the study. The primary care physician is always aware of the medication that receives the patient (single blind) and

will be the contact person and responsible to break the blind. Contact details are available in the patient information form. After unblinding, the responsible primary care physician will report it to the coordinating office of the project (ODDS, S.L., [contact]).

3.11. SAMPLE SIZE CONSIDERATIONS

For the main objective of the study, changes in mean nocturnal systolic blood pressure will be compared between the active treatment and placebo groups.

The use of SGLT2 inhibitors has been reported to be associated with reductions in office blood pressure of 4–8 mmHg, reductions that could be even higher with the use of ambulatory BP monitoring.¹⁵

Accepting an alpha error of 0.05 in a two-sided test, 150 patients are needed in the active treatment group and 75 in the placebo group (2:1 randomization) to have an 80% power (beta error=0.2) to detect as statistically significant a difference greater than or equal to 5 mmHg in mean nocturnal BP between placebo and active treatment (conservative estimate of the expected effect). The standard deviation is assumed to be 12 mmHg and it is expected a drop-out rate of 9%.

In the prespecified subgroup analysis by albuminuria levels, this sample size (75 in active treatment and 37 in placebo) allows to detect as statistically significant, within each albuminuria stratum and with the same assumptions and alfa and beta errors, a difference greater than or equal to 7,1 mmHg in the reduction of mean nocturnal BP between both groups (active treatment and placebo), an effect still within what can be expected.

3.12. DATA MANAGEMENT

Data will be collected in an electronic CRF by participating doctors and nurses both at the hypertension units and at primary care centers. A range of acceptable values and logical rules among variables will be implemented to improve quality of data and reduce the need of queries.

The processing, communication and transfer of data will be in accordance with the provisions of the Organic Law 15/1999, December 13th, on the protection of personal data.

Trial documentation will be kept and storaged in each site for 25 years after completion of the study.

3.13. PLAN OF ANALYSIS

The main analysis will compare baseline and final visit values of nocturnal blood pressure and all the rest of quantitative variables of interest within each stratum of albuminuria by means of paired t-test. Changes of nighttime blood pressure from baseline to final visit among patients with high and very high albuminuria levels will be compared to placebo with t-test.

Variables will be described by means of mean (and standard deviation) or proportion depending on the type of variable considered. Whenever the test of hypothesis may involve discrete variables, chi-squared test will be used.

Comparability of treatment and placebo groups will be tested (t-student or chi-squared test, depending on the variable) to assess randomization, and linear regression will be used to adjust for potential confounders, if needed; stratum of albuminuria at randomization will be forced in the model.

To respond to secondary objectives, the same analyses will be done for each stratum of albuminuria at randomization.

Only patients that complete the 3-month follow-up will be analyzed. Patients who do not complete the follow-up will be compared to those who adhere to the protocol.

No interim analysis is planned. A *p* value<0.05 will be considered as statistically significant.

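### The analysis named as main is a before-after paired t-test within albuminuria strata, not the overall dapagliflozin-versus-placebo comparison that the primary objective and sample size rest on

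*Combined protocol and SAP*

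**What the plan says.** Section 2 sets the primary objective as the effect of adding dapagliflozin, compared with adding placebo, on the 12-week change in nighttime BP. The two albuminuria subgroups are secondary objectives. Section 3.11 agrees: for the main objective, "changes in mean nocturnal systolic blood pressure will be compared between the active treatment and placebo groups".

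Section 3.13 opens differently: "The main analysis will compare baseline and final visit values of nocturnal blood pressure", together with all other quantitative variables of interest, "within each stratum of albuminuria by means of paired t-test". It does not say whether this is run separately by arm or with the arms pooled. The next sentence plans a t-test against placebo of the change in nighttime BP among patients with high and very high albuminuria. It is not called main or primary, and it names no variable other than nighttime BP. A later paragraph offers linear regression with albuminuria stratum forced in, but only if adjustment is needed. The section then adds: "To respond to secondary objectives, the same analyses will be done for each stratum of albuminuria at randomization".

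**The concern.** The contrast labelled main differs from the primary objective in two ways: it is before versus after rather than between arms, and it is done within each stratum rather than overall.

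A before-after fall can have causes other than the drug. Patients enter on raised office BP, HbA1c and albuminuria (section 3.2), so regression to the mean is expected directly for those variables and indirectly for nocturnal BP. Habituation to ABPM, placebo response and recorded changes in other medication (section 3.6) may add to it. Under the visit table in 3.20, office BP is taken in primary care at visit 0 and in hospital at week 12, so its paired test also absorbs a change of setting. This last point does not affect the primary endpoint, since both ABPMs are done at the hospital.

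What is at stake is which result is reported as the trial's finding. An analyst following 3.13 literally could present an uncontrolled change as primary, or could choose among several readings after seeing the data. For office BP, HbA1c and albuminuria, the paired test is the only comparison of change that the section specifies explicitly and without condition.

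**Working it through.** **Inputs from the documents.** Section 3.11: "Accepting an alpha error of 0.05 in a two-sided test"; 80% power; "a difference greater than or equal to 5 mmHg in mean nocturnal BP between placebo and active treatment"; "The standard deviation is assumed to be 12 mmHg"; 9% drop-out; 150 + 75 patients overall and 75 + 37 per stratum. Section 3.4: 2:1 allocation. Section 3.13: only completers are analysed.

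**Step 1: reproduce the planned sample size as a between-arm test.**

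- Placebo n = (1 + 1/2) × (1.96 + 0.8416)² × 12² / 5² = 67.8, so 68. Active n = 2 × 68 = 136.
- With drop-out: 68/0.91 = 74.7, so 75; 136/0.91 = 149.5, so 150. The total is 225, as stated.
- Stratum completers: 75 × 0.91 ≈ 68 and 37 × 0.91 ≈ 34. Detectable difference = 12 × √(1/68 + 1/34) × 2.8016 = 7.06 mmHg, against the stated 7.1.

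Both figures in 3.11 are therefore two-sample calculations. Neither was derived for a paired test.

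**Step 2: the paired test when the drug does nothing.** Assumptions: the SD of within-patient change is 12 mmHg (3.11 does not say whether its SD refers to change or to a single value), and all patients share a non-drug fall of m mmHg. The documents give no value for m, so a range is shown. The standard error in 68 dapagliflozin completers is 12/√68 = 1.455, and the noncentrality is m/1.455. The chance in at least one of two strata is 1 − (1 − p)².

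| Shared fall m (mmHg) | Dapagliflozin arm, one stratum (n = 68) | At least one of two strata | Arms pooled, one stratum (n = 102) |
|---|---|---|---|
| 2 | 0.27 | 0.47 | 0.39 |
| 3 | 0.53 | 0.78 | 0.71 |
| 4 | 0.77 | 0.95 | 0.92 |

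With an SD of change of 15 instead of 12, the first column becomes 0.19, 0.37 and 0.58. The between-arm t-test stays at 0.05 throughout, provided the non-drug change is the same in both arms.

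Pooling the arms also distorts a real effect. With 2:1 allocation and no change on placebo, a true 5 mmHg effect appears as 5 × 2/3 = 3.3 mmHg.

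**Step 3: the placebo t-test, overall or per stratum.** Power at 5 mmHg from the noncentral t distribution, SD 12:

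- Overall, 136 versus 68: standard error 12 × √(1/136 + 1/68) = 1.78; power 79.7%.
- One stratum, 68 versus 34: standard error 12 × √(1/68 + 1/34) = 2.52; power 50.2%.
- Two unadjusted stratum tests at 0.05 with no effect in either: 1 − 0.95² = 9.75%.

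**The case against.** The strongest reply is that the randomised comparison is in the plan. Section 3.11 ties it to the main objective, section 2 does the same, and the sentence in 3.13 directly after the paired test compares changes with placebo. The paragraph can be read as two steps, first within group and then against placebo. On that reading the strata are plainly secondary: 3.11 calls them a subgroup analysis and already discloses 7.1 mmHg as their detectable difference, and forcing stratum into a regression makes sense only with the strata combined. The probabilities in step 2 also depend on an assumed fall, and they become false claims of drug effect only if the placebo comparison is set aside.

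Much of this is fair. The comparison is not missing; the fault lies in which analysis is named main. The 50% power and 9.75% error apply only under the per-stratum reading. Regression to the mean is indirect for nocturnal BP, because entry is on office BP.

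The defect nonetheless remains. The placebo test is not labelled main, can be read as one test or two, and covers nighttime BP only. The sentence repeating the same analyses by stratum implies an overall main analysis, yet the analysis called main is already within stratum. Section 3.13 nowhere clearly names the test that 3.11 powers.

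**Conclusion.** The concern holds and should be fixed before any analysis. Section 3.13 gives the title of main analysis to an uncontrolled before-after test that does not estimate the effect in the primary objective and does not control the false-positive rate for it. Under no drug effect, that rate would be about 27% to 77% per stratum in the dapagliflozin arm for an assumed shared fall of 2 to 4 mmHg and an SD of change of 12. Those figures illustrate the exposure; they are not forecasts. That the label conflicts with sections 2 and 3.11 does not depend on them.

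**What to change.** Rewrite the first paragraph of 3.13 along these lines:

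- **Primary analysis:** one comparison, dapagliflozin minus placebo with both albuminuria strata combined, of the change in nocturnal systolic BP from week 0 to week 12, two-sided at 0.05, with a 95% confidence interval. If a linear model is preferred to the t-test, for example with baseline value and albuminuria stratum, name it now as the primary method rather than leaving it to be used if needed.
- **Secondary analyses:** the same between-arm comparison within each stratum, and between-arm comparisons of change in office BP, HbA1c and albuminuria.
- **Paired before-after tests:** descriptive only, reported by arm, and supporting no efficacy claim.

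The cost is a wording change in 3.13. The sample size was already calculated for this test and stays at 225 (150 + 75), with about 80% power for 5 mmHg. No new data, visits or patients are needed.

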3.4. RANDOMIZATION

Two strata will be considered based on albuminuria levels:

- High albuminuria (30-300 mg/g creatinine)
- Very high (>300 mg/g creatinine)

Patients will be randomized to either dapagliflozin or placebo in a 2:1 ratio.

Figura 2.-Randomization scheme

Total number of patients: 225; distributed as:

- 150 diabetic patients treated with dapagliflozin (10mg/day in a single dose), half of them with high albuminuria levels (albuminuria 30-300 mg/g of creatinine) and half with very high albuminuria levels (albuminuria > 300 mg/g of creatinine)

- 75 diabetic patients treated with placebo, half of them with high albuminuria levels (albuminuria 30-300 mg/g of creatinine) and half with very high albuminuria levels (albuminuria > 300 mg/g of creatinine)

Randomization will be stratified by albuminuria strata and participating hospital (three hospitals); center specific randomization lists (active treatment or placebo) will be prepared centrally at the project office with a treatment code assigned to each patient.

Allocation will be concealed by means of sequentially numbered, opaque, sealed envelopes that contain the medication code assigned. The envelopes have to be opened sequentially and only after the participant's name is written on the appropriate envelope.

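### The between-arm test is an unadjusted t-test on change, with adjustment left to an undefined condition; one prespecified ANCOVA on baseline nocturnal BP would be more precise at no extra data cost

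*Combined protocol and SAP*

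**What the plan says.** The primary endpoint in section 3.8 is the change in mean nocturnal BP from week 0 to week 12. Section 3.11 sizes the trial on nocturnal systolic BP.

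For the comparison between arms, section 3.13 says that changes "among patients with high and very high albuminuria levels will be compared to placebo with t-test". It continues: "Comparability of treatment and placebo groups will be tested (t-student or chi-squared test, depending on the variable) to assess randomization", and then, in the same sentence, "linear regression will be used to adjust for potential confounders, if needed; stratum of albuminuria at randomization will be forced in the model". It gives no criterion for the condition, no list of confounders, and no statement of which between-arm result is primary.

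Two other places bear on the point. Section 3.4 says: "Randomization will be stratified by albuminuria strata and participating hospital (three hospitals"). Section 3.9 says that "ABPM and blood and urine samples will be obtained on visits 0", and ABPM is repeated at week 12. So hospital and baseline nocturnal BP are both available for every randomised patient, yet section 3.13 names neither as a covariate. Albuminuria stratum is named, but only for the regression.

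**The concern.** There are two separate problems.

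**Precision.** A change score uses the baseline reading by subtraction, which fixes its coefficient at 1. ANCOVA estimates that coefficient, and the estimated value minimises the residual variance. Whenever the two visits are imperfectly correlated and equally variable, the t-test on change gives away information already collected. This matters most in the two albuminuria strata. There the plan can detect only 7.1 mmHg, against the 4-8 mmHg office BP reduction that section 3.11 cites.

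**Prespecification.** With the adjusted or unadjusted choice left open, the type I error depends on how the choice is made. The clause on testing comparability suggests, without saying so, that baseline significance tests would decide. Under randomisation such a test on baseline BP is significant in about 5% of trials by chance, so that route would almost never recover the lost precision. A freer choice, made after seeing both results, would be anti-conservative.

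**Working it through.** **Inputs.** From section 3.11: two-sided alpha 0.05, power 80%, difference 5 mmHg, SD 12 mmHg, 9% drop-out, 150 and 75 patients. From section 3.13: completers only. The correlation r between baseline and week-12 nocturnal BP is not in the documents; it is an assumption, shown for 0.3 to 0.8. Section 3.11 does not say whether 12 mmHg is the SD of change or of a single reading, so both are shown.

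**The plan's own figures.** Placebo n = (1.960 + 0.842)² × 12² × (1 + 1/2) / 5² = 67.8, so 68, with 136 active. Dividing by 0.91 gives 75 and 150, total 225, as stated. Power of the t-test with 136/68 completers (noncentral t, 202 df) is 79.7%. Within a stratum, with 68/34 completers, the detectable difference is 2.802 × 12 × √(1/68 + 1/34) = 7.06 mmHg, matching the stated 7.1.

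**Gain from ANCOVA.** With SDs s1 at baseline and s2 at week 12, the change-score variance is s1² + s2² − 2·r·s1·s2 and the ANCOVA residual variance is s2²(1 − r²). The difference is (s1 − r·s2)², which is never negative. With s1 = s2 the ratio of ANCOVA to change-score variance is (1 + r)/2.

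*Case A: 12 mmHg is the SD of change.* ANCOVA SD = 12 × √((1 + r)/2). Power is at 5 mmHg with 136/68 and 198 df. The last column is 204 × (1 + r)/2.

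| r | ANCOVA SD | Power (t-test 79.7%) | Within-stratum detectable difference, mmHg (t-test 7.06) | Completers matching the planned 204 |
|---|---|---|---|---|
| 0.3 | 9.67 | 93.4% | 5.69 | 133 |
| 0.5 | 10.39 | 89.7% | 6.12 | 153 |
| 0.7 | 11.06 | 85.7% | 6.51 | 173 |
| 0.8 | 11.38 | 83.7% | 6.70 | 184 |

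*Case B: 12 mmHg is the SD of one reading.* Change SD = 12 × √(2(1 − r)); ANCOVA SD = 12 × √(1 − r²).

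| r | Change SD | t-test power | ANCOVA SD | ANCOVA power |
|---|---|---|---|---|
| 0.3 | 14.20 | 65.5% | 11.45 | 83.3% |
| 0.5 | 12.00 | 79.7% | 10.39 | 89.7% |
| 0.7 | 9.30 | 95.0% | 8.57 | 97.4% |
| 0.8 | 7.59 | 99.3% | 7.20 | 99.7% |

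**Hospital.** The documents do not show that hospital is prognostic. If it explained an assumed 2% to 10% of the variance, adding it alone would move power from about 80% to about 81-84% (normal approximation).

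**Type I error.** Null simulation with bivariate normal readings, 136/68, 100,000 trials for each r, and baseline nocturnal BP as the covariate. The Monte Carlo standard error near 5% is √(0.05 × 0.95/100,000), about 0.07 percentage point.

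| Rule | r = 0.3 | 0.5 | 0.7 | 0.8 |
|---|---|---|---|---|
| t-test alone | 5.1% | 5.0% | 5.1% | 5.0% |
| ANCOVA alone | 4.9% | 5.0% | 5.0% | 5.1% |
| ANCOVA only if baseline differs at p<0.05, otherwise t-test | 4.1% | 4.3% | 4.7% | 4.7% |
| Success if either is significant | 7.7% | 7.3% | 6.9% | 6.5% |

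The baseline test triggered adjustment in 4.9-5.0% of simulated trials.

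**The case against.** The strongest reply is that nothing here is invalid. The t-test on change is unbiased under randomisation, the sample size was set for that test, and the trial is labelled a pilot. ANCOVA would therefore add efficiency beyond a target already met. That is correct, and it is why this is a recommended improvement and not an error in the trial's answer. But the trial is powered at 80% and declares significance at p<0.05, so its deciding model still needs to be fixed in advance.

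The sentence on regression can also be read differently: the condition may govern only the extra confounders, with a stratum-adjusted model always fitted. The wording allows this. Even so, baseline BP and hospital are still not named, and the primary result is still not identified.

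The size of the gain depends on assumptions. Holding the SD of change at 12 mmHg while r runs from 0.3 to 0.8 implies a single-visit SD from 12/√1.4 = 10.1 to 12/√0.4 = 19.0 mmHg. Unequal variances matter too: with r = 0.8 and s2/s1 = 1.1 (assumed), the variance reduction is (1 − 0.88)²/0.45, about 3% instead of 10%, and it vanishes at s2/s1 = 1.25. These points limit the amount. They do not reverse the direction, because the gain is a square.

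Finally, no passage proposes reporting the better of two results, so 6.5-7.7% describes what the open wording permits and not what is planned. The rule the text hints at is slightly conservative. Both points stand.

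**Conclusion.** The concern holds. Section 3.13 does not fix a single between-arm model, and the test it does name makes less than full use of the baseline ABPM.

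In Case A the power gain is between 4 and 14 percentage points across r = 0.8 to 0.3, equal to a 10-35% cut in variance. In Case B it ranges from under 1 point at r = 0.8 to 18 points at r = 0.3. These sizes rest on the assumed r, equal variances, and the reading of the 12 mmHg. The direction rests on none of them, apart from a trivial cost in degrees of freedom. Any benefit from hospital is probably small, and leaving it out is conservative; the case rests on baseline BP and on settling the model beforehand.

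**What to change.** Prespecify one primary between-arm analysis: ANCOVA of week-12 (or change in) mean nocturnal systolic BP on treatment, baseline nocturnal systolic BP, albuminuria stratum and hospital, reporting the treatment estimate with its 95% CI. Within an albuminuria stratum, use the same model without the stratum term. Use the same form for office BP, HbA1c and albuminuria, each with its own baseline; analyse albuminuria on the log scale, since permitted entry values span a hundredfold range (30 to 3000 mg/g).

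Remove the conditional trigger for adjustment. Describe baseline characteristics by arm without significance tests. Keep the unadjusted t-test as a supportive analysis.

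The cost is analysis-plan wording; no patient, visit or measurement is added. Residual degrees of freedom fall by 4 (202 to 198 with 204 completers), which changes power by less than 0.1 percentage point. The change should be dated before anyone examines outcomes by arm, because section 3.5 gives investigators the treatment codes.
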